to intervention protocol an internal process evaluation will be implemented each week for corrective feedback and adjustment as needed, and a booster training session for all staff will be implemented at mid-point. There is little-to-no communication across ASP sites (each site has their own staff and serve youth from distinctly separate schools), however to limit cross-contamination between study sites we will enlist the help of the program directors who have previous experience with other RCTs and possess a strong understanding of the importance of having distinct intervention and control conditions. These strategies have been highly successful in our previous studies.²⁵⁻²⁷

Study Measures

All study measures will be collected by trained and certified staff blind to group assignment. The PI will hire a Program Coordinator to assist with oversight and training of measurement staff. Measurement certification entails reviewing protocols and demonstrating agreement with the Coordinator on anthropometrics, systematic observations, survey protocols, and PA assessments. Our team has experience developing and using these protocols in large scale studies.²⁵ **See Appendices for all measures.**

Primary Aim 2. Feasibility

To test the feasibility of intervention implementation, **process evaluations** that monitor dose and fidelity will be conducted within both the intervention and control conditions once a week by an independent process evaluator for the duration of the program (**see Appendix B**). Through observation and use of a quantitative checklist and rating scales, the process evaluator will assess whether there are any changes in the structure, delivery, or climate of the control condition (e.g., whether youth are consistently provided at least 1 hour of daily free play), and whether the social climate of intervention ASPs achieve the program's essential elements.

Systematic observations will be conducted using the System for Observing Children's Activity and Relationships during Play (SOCARP; **see Appendix F**)^{73,74} and a modified version of the System for Observing Fitness Instruction Time (SOFIT) that includes a social climate observation tool that has been developed and tested by the PI (MCOT-PA).²⁹⁻³¹ Teams of two coders will make continuous observations of daily activities throughout 5 program days at each ASP. Observations will be used to assess changes in key social climate features for promoting youth affiliation goals. Staff structured interviews (**Readiness Assessment**) will assess staff perceptions of the feasibility and acceptability of the intervention program components conducted at baseline, mid-point, and post-intervention. This readiness assessment is developed to correspond with a multi-component theory of organizational readiness that addresses both program motivations and capacities⁷⁵ including motivation for implementing the CONNECT intervention, innovation-specific capacity for CONNECT, and general capacity, and has been previously piloted with principals, teachers, and technology specialists for a school-based technology intervention. We have adapted the assessment to fit within the afterschool program structure and PA goals of our intervention (**see Appendix H**).

The Social Motivational Orientations Scale for Sport (SMOSS)²³ will be used to assess changes in participants' degree of social affiliation orientation (7 items) and social validation orientation (8 items) toward PA (5-point scale, $M=2.44$; $SD=1.04$). The SMOSS is well-validated,^{23,76} correlated with PA value, enjoyment, and perceived ability, and has adequate internal consistency (reliability coefficients range from .77 to .87). **The Motivation for Physical Activities Measure (MPAM)** assesses five motives for participating in PA: Fitness, Appearance, Competence/Challenge, Social, Enjoyment. The scale has been used to predict various behavioral outcomes, such as attendance, persistence, or maintained participation in some sport or exercise activity, and to predict mental health and well-being and has demonstrated strong internal consistency (alphas above .87 for each of the subscales)⁷⁷ **The**

Task and Ego Orientation in Sport Questionnaire (TEOSQ) assesses youth task (mastery) or ego (performance) orientations towards PA and is predictive of value, intrinsic interest and enjoyment in PA (reliability coefficients range from .71 to .87)⁷⁸. **The Need for Relatedness Scale**⁷⁹ will assess feelings of social connections to others within the ASP setting and has been previously validated using other SDT constructs⁸⁰⁻⁸² (reliability coefficients range from .86 to .92; 5-pt scale, $M=3.74$; $SD=.75$). The **Perceived teacher support scale**⁸³⁻⁸⁵ (reliability coefficient =.84; 5-pt scale, $M=3.22$; $SD=1.05$) and **The Peer Motivational Climate in Youth Sport Questionnaire**⁸⁶ (reliability coefficients range from .69 to .82; 7-pt scale, $M=3.18$, $SD=1.32$) will be used to measure youth perceptions of staff and peer connections. Validity of both measures has been supported in previous work and shown to correlate with PA enjoyment, effort, and prosocial and social responsibility goals.⁸³⁻⁸⁶ **The Social Support and Exercise Survey** will measure changes in youth family and friend social support for youth PA.⁸⁷ (See Appendix G for Youth Survey Measures).

Secondary Aims 1, 2, and 3: Youth MVPA, Cognitions, Affect, and BMI

Youth Physical Activity (Accelerometer). Objective assessments of PA will be obtained on youth with omni-directional accelerometers (Acticals; Mini-Mitter, Bend, OR).⁸⁸ Actical has demonstrated correlations between activity counts and energy expenditure of individuals measured concurrently with accelerometers (e.g., MTI Actigraph, Caltrac, Tritrac) in several studies.⁸⁹ Youth will wear an accelerometer over 7 consecutive days to calculate PA at baseline, endpoint, and post-intervention. Data will be recorded in 30-s epochs to best capture short bouts of vigorous activity,^{90,91} and raw activity data will be converted into time spent in moderate (3-5.9 METS), vigorous (6-8.9 METS), and MVPA (3-8.9 METS) based on activity count thresholds for children identified by Puyau et al.⁸⁸ [name] (PI) and [name] (Co-I) have been involved in multiple trials using accelerometer to measure PA in youth.²⁵⁻²⁷

PA Cognitions will be measured by **youth perceptions of their physical ability** (5-pt scale, $M=3.68$; $SD=.97$) and **value of PA** (5-pt scale, $M=3.81$; $SD=1.18$) using four items derived from the expectancy-value model that have been well-validated in youth minority populations⁹²⁻⁹⁴ (reliability coefficients range from .76 to .94). PA Affect will be measured by the extent to which adolescents engaged and enjoyed PA activities using **The Intrinsic Interest Scale**⁹⁵ (reliability coefficients from .83 to .94; 5-pt scale, $M=3.7$, $SD=1.0$) and the degree to which youth are concerned about performing well during PA using the worry subscale of **The Sport-Anxiety Scale-2** (reliability coefficient = .89; test-retest = .90; sum score range 4 to 20; $M= 12.12$; $SD=3.85$).⁹⁶ All PA cognition and affect measures have been shown to be correlated with the SMOSS and other measures of interest to the study (e.g., PA effort, ability).^{23,76,96} **Body Mass Index.** Height and weight will be measured at baseline and post intervention using a Shorr Height Measuring Board and a SECA 880 digital scale. Sex- and age-standardized BMI (zBMI) will be calculated for youth using CDC 2000 reference curves. (See Appendix G for Youth Survey measures).

Covariates. Demographic data will be collected on adolescents at baseline including self-report age (date of birth), race/ethnicity, and gender. Free /reduced lunch status will be derived from school/program records. The Positive Youth Development Scale (PYD-VSF; reliability coefficients from .72 to .90)⁹⁷ and The Strengths and Difficulties Questionnaire (SDQ; test-retest reliability=.80)^{98,99} will be used to measure indicators of positive development (e.g., connection, competence) and the presence of depressive symptoms because of previous research indicating an association between well-being/depression and youth PA and obesity. Lastly, the Self-Regulation Questionnaire- Prosocial (SRQ-Prosocial) assesses individual differences in prosocial behaviors, friendship, interpersonal skills, and exercise (reliability coefficients from .61-.85).¹⁰⁰

E. Analysis Plan

This proposal is a feasibility test of the social climate intervention and will gauge a plausible effect size of the program for a larger R01 application. To that end, we will examine several subjective and objective markers of program success such as changes in targeted social mechanisms within youth and the ASP climate, and explicit PA outcomes. We will also explore the potential effects of the intervention on youth BMI. Although only minimal change in BMI would be plausible given the length of the current proposal, our findings will have implications for impacting BMI as the targeted outcome of a larger R01 trial.

Primary Aim 1. (ADDRESSED). The first aim of the study is to conduct qualitative interviews with program staff and youth to identify conceptual constructs most relevant for fostering youth PA affiliation orientation. Interviews and focus groups will be transcribed, coded, and analyzed (QSR NVivo) to identify common themes for these study goals. A coding scheme composed of “levels” of categorization or manageable “themes,” will be developed to guide the manner in which the qualitative data will be analyzed. Ultimately, these themes will be used to summarize the data. Data will be coded by two coders and inter-rater reliability estimates will be assessed. Prior to analysis, raters will meet to discuss each coding disagreement until consensus is met regarding final codes. The PI has extensive experience in using QSR NVivo to conduct content analysis of themes (see our previous work).²⁸

Primary Aim 2. The second primary aim of the study is to assess whether youth in the intervention demonstrate greater change in the 3 PA social affiliation mechanisms from baseline to post-intervention. Gains in these social mechanisms will be assessed with repeated measures ANCOVA models in which time (baseline to end of program and baseline to post-intervention) is a within subject factor and treatment is a between subjects factor for social mechanism variables measured in both conditions. Analyses will control for demographics, baseline BMI, and any other variables for which there are baseline differences between treatment and control groups (e.g., PYD, depression). To examine overall changes in social mechanisms within the intervention alone, similar repeated measures ANCOVAs will be used, with the between subjects treatment factor dropped. The test of interest will be the within subjects factor of time, with affiliation goals expected to improve over time. Process Evaluation, used to assess the quantity (dose) and quality (fidelity) of program implementation, will also serve as feasibility assessments. Our group has extensive experience with “dose-response” analyses.²⁷ Weekly observational assessments of program facilitation, using standardized ratings developed for other studies,¹⁰¹⁻¹⁰³ will be reduced to a total score, indicating overall fidelity to the activity observed.

Secondary Aims. **Secondary Aims 1 and 2** tests the a-priori hypothesis that youth in the intervention (vs. comparison) will have greater improvements in PA affect, cognitions, and MVPA and healthier BMI (z-score) trajectories (e.g., slight reduction; less increase) from baseline to post-intervention. This study will also provide us with information on the effect size that might be expected to power an efficacy trial after completion of the R21 project. Greater improvements will be assessed with several repeated measures ANCOVA models in which time (baseline to post-) is a within subject factor and treatment is a between subjects factor for PA variables measured in both conditions. Analyses will control for demographics (and BMI for PA outcomes) and other variables for which there are baseline differences between treatment and control groups. Multiple imputation protocols^{104,105} will be used to address missing accelerometer data (see our previous work).²⁵

Secondary Aim 3 explores whether changes in youth PA social orientations mediate the effect of the intervention on changes in adolescent PA outcomes. This hypothesis will be tested with a

multiple mediator model (estimated path model) where the indirect effect of the program on PA through social mechanisms will be examined. Bootstrapped estimates of the mediated effect will be examined in line with recommendations from methodological research.^{106,107} Both the total indirect effect of all variables together and specific mediated effects of each variable will be examined.

F. Human Subjects

Protection of Human Subjects

Risks to the Subjects

Human Subjects involvement and Characteristics. Subjects will be healthy male and female adolescents and adults. To be eligible, adolescents must 1) be currently enrolled in the afterschool program, 2) have parental consent to participate, and 3) agree to study participation and random assignment, and 4) be available for baseline and post-intervention measurement. Adolescents will be excluded from participation if 1) have a medical condition that would interfere with the prescribed physical activity intervention plan, 2) are developmentally delayed such that the intervention materials will not be appropriate or, 3) are in treatment for a psychiatric disorder. To be eligible, adults must 1) be part of the afterschool staff, 2) have no medical condition or disorder that would limit participation, 3) be available and able to participate in the interviews and/or the intervention phase for the study period.

Sources of Material. All data will be obtained for research purposes only. Data collected for adolescents will be demographic (age, race, date of birth), anthropometrics (height and weight), behavioral (physical activity as measured by accelerometer estimates), and psychosocial surveys related to changes in physical activity affect, cognitions, behaviors, and general well-being. Data collected for adults will include demographics (age, race, etc.), and structured interviews to ask about their views on the best methods for engaging staff in program goals and for adopting the intervention into their pre-existing program and assess what supports are needed to increase the quality of implementation and sustainability of the program post-intervention. Distinct program dimensions measured include motivation for implementing the CONNECT intervention, innovation-specific capacity for CONNECT, and general capacity (**see Appendix H**). The interview protocol also includes measurement of staff motivation, value, and perceived efficacy for implementing the intervention curriculum and PA more generally. Interviews will be tape recorded and transcribed and names will not be included with the participants' recorded responses.

Potential Risks. There is little risk involved in participating in this study. Typical to any Physical Education class (PE) subjects who participate in the intervention may experience some discomfort such as minor physical strains and sprains associated with engaging in physical activities during the intervention. Activities offered in both the health class and the afterschool program are similar in risk to the typical activities offered in the class/afterschool program. There is little risk associated with wearing the accelerometers in the study. Adolescents will be monitored to determine if they are experiencing any discomfort as a result of wearing the devices. There is also little risk to filling out the questionnaires – the majority of questions are centered on PA (social) preferences and perceptions about their experiences in the program, and are not anticipated to trigger negative emotional states. Adolescents will be encouraged to skip a question or stop filling out the questionnaire if they feel any discomfort with questions asked. Numbers will be provided to each adolescent so that their questionnaire cannot be identified, and the names-to-numbers list will be kept separate from participants' recorded responses. The data collected from youth will be kept confidential in all circumstances unless information acquired about a child's wellbeing indicates the child may be at harm. In such a case, we would privately contact the parent and refer the child to the school counselor for further assessment. This breach of confidentiality is articulated in the consent form.

Adequacy of Protection Against Risks

Recruitment and Informed Consent. All program staff from each of the 7 afterschool programs (the health program control administered during the school day in y1 will be excluded) will be asked to participate in the interview component of the study (N=21). Informed consent will be sought from each adult for participation in this project.

A total of 298 students in the select afterschool programs will be recruited to participate in the study (Y1 Pilot study = 98 students; Y2 Intervention = 200 students). Adolescents will be excluded from participation if they 1) have a medical condition that would interfere with the prescribed physical activity intervention plan, 2) are developmentally delayed such that the intervention materials will not be appropriate or, 3) are in treatment for a psychiatric disorder. Informed consent will be sought from each child's parent/guardian for participation in this project. Assent forms will also be completed by all students prior to participating in the study. Parents and children will be encouraged to ask any questions they might have regarding the procedures. There will be no coercion to participate or prejudice against those who choose not to take part in the study. We will submit an application to the University of South Carolina Institutional Review Board for approval of study procedures and the informed consent protocol. No data collection will take place prior to IRB approval.

Protection Against Risk. There is little risk associated with wearing the physical activity monitors in this study. Adolescents will be monitored to determine if they are experiencing any discomfort as a result of wearing the devices. Safety and prevention of injury while wearing the monitors will be considered. Likewise, there is little risk associated with participating in the physical activities. Risks are parallel to a typical PE class and are similar to the risk of the typical activities offered in the class/afterschool program. Staff from the University of South Carolina will be available to assist with any minor injuries as a result participating in the physical activities during the program. All school-based ASP staff are trained in CPR and intervention staff will be trained by PA leaders (hired PE teachers) on injury prevention during the pilot study and randomized intervention study. The majority of staff interview questions and youth questionnaires will be centered on PA (social) preferences and perceptions about their experiences in the program and the proposed intervention, and are not anticipated to trigger negative emotional states (see above for details). Participants will be encouraged to skip a question or dismiss themselves from the interviews or questionnaires if they feel any discomfort with questions asked. Data will be kept completely confidential unless a child provided information that indicates he/she may be at harm (e.g., depression). In such a case, we will privately contact the school counselor and caregiver. Numbers will be provided to each participant so that they are not addressed by name in the recorded interview, and the names-to-numbers list will be kept separate from participants' recorded responses. Similarly, youth names will be kept separate from their questionnaires, and the names-to-numbers list will be stored in locked file cabinets. Data collected in this study will be accessed only by the investigators and designated staff persons. Staff that collect study measurements will be trained and supervised by the PI and program coordinator on the proposed project. Data will be stored in locked file cabinets that only study staff can access. Additionally, electronic participant databases will be password protected and stored at the University of South Carolina. Afterschool program personnel will not have access to the data. We have used these procedures on several research studies to successfully protect against risk.

Potential Benefits of the Proposed Research to the Subjects and Others. The goal of the proposed study is to assess the feasibility of developing an afterschool program climate that increases and sustains youth moderate-to-vigorous physical activity and improves youth body mass index (BMI) trajectories through meeting youth social developmental needs. The findings from this study will provide the information necessary to conduct a large scale efficacy trial that

could have important implications for increasing the potential impact of afterschool-based health interventions for preventing obesity.

Adult participants in this study will learn valuable information about how to improve the afterschool climate to support student engagement in physical activity, and will be provided valuable strategies and tools that they can implement within their programs. Psychosocial benefits for both students and adults include improved relationships within the program (including between staff, between students, and between staff and students), improved afterschool program supports for health initiatives, and valuable opportunities and strategies for improved physical activity. Physical benefits of the proposed research for youth (and, indirectly, adults) will include weight control, building muscle mass, reducing fat, lowering blood pressure, and reducing psychosocial symptoms of depression and anxiety. Thus, increasing physical activity in adolescents (and, indirectly adults through intervention implementation) may have important public health implications for reducing chronic disease and increasing longevity and quality of life in this population. The benefits of the proposed research to the adult and adolescent participants outweigh the potential risks.

Importance of the Knowledge to be Gained. Results will fill knowledge gaps and provide feasibility for a larger afterschool-based efficacy trial that will implement a social climate that 1) facilitates youth perceived connectedness and affiliation goal orientations during PA; 2) improves youth PA-related affect, cognitions and behaviors to reduce youth body mass index (BMI), and 3) sustains behavior changes post intervention for continued improvements in BMI trajectories. The results from this study will have important implications for increasing the effectiveness of afterschool interventions/programs for obesity prevention among underserved youth.

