Targeted Population, Recruitment, and Retention. We aim to recruit 8 middle-school ASPs located within a 70 mile radius of Columbia that serve a primarily underserved population of middle school youth (6th-8th grade) youth. All ASP sites will need to include 1 hour of daily PA/freeplay as one component of the curriculum and be similar in size, percentage of youth per site on free or reduced lunch, race, and gender. One ASP will be asked to participate in the pilot during year 1 and will be compared to a school-based control (youth in the control will receive our general health curriculum administered in their health class during the school day). During year 2, six ASPs will be randomized to the treatment or control (general health curriculum) conditions after baseline data collection. ASP staff and all youth enrolled in the program will be asked to participate in the study. To be eligible, youth must 1) be enrolled in the ASP, 2) have parental consent and assent to participate, and 3) be available for baseline and post-intervention measurement. Youth will be excluded from participation only if they have a medical condition that would interfere with the program's prescribed PA.

Overview of Intervention.

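### Arms are compared on change from baseline, although the baseline outcome is collected before randomization and could be conditioned on; the likely precision gain is modest and, with six sites, not guaranteed

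*Combined protocol and SAP*

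**What the plan says.** Section E (Analysis Plan), Primary Aim 2, specifies repeated measures ANCOVA in which "time (baseline to end of program and baseline to post-intervention) is a within subject factor and treatment is a between subjects factor". Secondary Aims 1 and 2 repeat the structure: "time (baseline to post-) is a within subject factor and treatment is a between subjects factor for PA variables". Both are worded as larger change or improvement in the intervention arm.

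The Primary Aim 2 covariates are demographics, baseline BMI and "any other variables for which there are baseline differences between treatment and control groups (e.g., PYD, depression". For the secondary aims the text is "Analyses will control for demographics (and BMI for PA outcomes) and other variables for which there are baseline differences". Neither list includes the baseline value of the outcome being analysed, and no common baseline mean across arms is imposed. For zBMI there is no planned baseline adjustment, because BMI is a covariate for PA outcomes only.

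Section D (Targeted Population, Recruitment, and Retention) says that "six ASPs will be randomized to the treatment or control (general health curriculum) conditions after baseline data collection", and that youth must "be available for baseline and post-intervention measurement" to be eligible. The opening of Section E gives one purpose of the study as gauging an effect size for a larger application.

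**The concern.** When baseline is one level of the within-subject factor, each arm-by-time contrast from baseline is a difference in mean change. Section E does not name the arm-by-time interaction as the between-arm test, but the model structure and the wording of the aims imply it.

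A change score subtracts the whole baseline value. Conditioning subtracts only the part that predicts follow-up. Because baseline precedes randomization, conditioning on it is legitimate and, with independent youth, never less precise. At stake is the precision of the effect estimates meant to inform the larger trial.

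**Working it through.** **Stated figure.** Section D gives 200 youth in six ASPs, three per arm, with no power calculation. There is nothing to reproduce.

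**Inputs.** 200/6 is about 33 youth per ASP. Rho (youth level, within ASP), the ICC (equal at both waves) and the ASP-level correlation between waves (rc) are not in the documents; all are assumed. Outcome variance is set to 1.

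**Step 1: ignoring clustering.** The change-score variance is proportional to 2(1 − rho) and the baseline-adjusted variance to 1 − rho². The SE ratio is therefore √((1 + rho)/2).

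| rho | SE ratio | SE reduction |
|---|---|---|
| 0.3 | √0.65 = 0.806 | 19% |
| 0.5 | √0.75 = 0.866 | 13% |
| 0.7 | √0.85 = 0.922 | 8% |
| 0.9 | √0.95 = 0.975 | 2.5% |
| 0.95 | √0.975 = 0.987 | about 1% |

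The last row is an assumed value for zBMI, which may be very stable over this interval.

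**Step 2: what the reliabilities suggest.** Section D (Study Measures) gives "reliability coefficients range from .77 to .87" for the SMOSS, "reliability coefficients range from .69 to .82" for peer climate, .84 for teacher support and a test-retest value of .90 for worry. If rho cannot exceed reliability (errors uncorrelated across waves, assumed), 1 − √((1 + r)/2) gives 8.1% at .69, 5.9% at .77, 4.6% at .82, 4.1% at .84, 3.3% at .87 and 2.5% at .90. These figures hold only without clustering.

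**Step 3: six ASPs of 33, youth-level adjustment with slope rho.**

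- Var(change) = (2/3)[2·ICC·(1 − rc) + 2(1 − ICC)(1 − rho)/33]
- Var(adjusted) = (2/3)[ICC·(1 + rho² − 2·rho·rc) + (1 − ICC)(1 − rho²)/33]

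Example at rho 0.5, ICC 0.05, rc 0.8: change is (2/3)(0.0200 + 0.0288) = 0.0325, SE 0.180; adjusted is (2/3)(0.0225 + 0.0216) = 0.0294, SE 0.171.

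| rho 0.5: ICC | rc | SE, change | SE, adjusted | Adjusted vs change |
|---|---|---|---|---|
| 0.02 | 0.8 | 0.159 | 0.144 | 9% lower |
| 0.05 | 0.8 | 0.180 | 0.171 | 5% lower |
| 0.05 | 0.9 | 0.161 | 0.161 | unchanged |
| 0.10 | 0.9 | 0.178 | 0.192 | 8% higher |

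Simulation of the same layout (20,000 runs) gave 0.158 vs 0.144, 0.178 vs 0.171, 0.162 vs 0.161 and 0.177 vs 0.191. The most adverse setting simulated (rho 0.3, ICC 0.10, rc 0.9) gave 0.197 for change against 0.225 (pooled slope) or 0.232 (within-ASP slope), which is 14% to 18% higher.

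The Step 2 figures do not survive as minima. At rho 0.84, ICC 0.05 and rc 0.9, the gain is √((0.00968 + 0.00848)/(0.01000 + 0.00921)) = 0.972, or 2.8%, not 4.1%. At ICC 0.10 and rc 0.95, adjustment is 0.7% worse.

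**Step 4: break-even.** Setting the two variances equal gives rc = (1 + rho)/2 + (1 − ICC)(1 − rho)/(2·33·ICC). Above this value the change score is the more precise.

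| rho | ICC 0.05 | ICC 0.10 |
|---|---|---|
| 0.3 | 0.85 | 0.75 |
| 0.5 | 0.89 | 0.82 |
| 0.7 | 0.94 | 0.89 |
| 0.84 | 0.97 | 0.94 |

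At ICC 0.02 the formula exceeds 1 for each of these rho values (1.12 at rho 0.5), so there is no break-even.

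**Step 5: the add-on covariate rule.** With PYD and SDQ as two independent candidates and an assumed 5% youth-level test, at least one enters in 10%, 23% and 40% of simulated trials at ICC 0, 0.02 and 0.05. Selecting them rather than always including them ranged from about 1% less noisy to 2.5% noisier.

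**The case against.** Change scores are a valid analysis, and the aims are worded in terms of change. With three sites per arm and no rho, ICC or ASP-level correlation in the documents, even the direction of the precision difference is an assumption. This stands. It limits the point to a recommended default with a named downside.

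A reader might infer that a change score can never be the more precise choice. That is true for independent youth, but Step 3 shows it fails when ICC and ASP-level correlation are both high. A reader might also take the quoted reliabilities as guaranteeing a minimum gain. They describe the instruments, not the correlation over the study interval or between sites, and they give no such guarantee here.

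It could be said that the label ANCOVA already implies baseline adjustment. The listed covariates do not bear this out: the outcome's own baseline could enter only if it happened to differ between arms.

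On covariates, a reader might infer that the whole adjustment set is undefined. It is not. Section E fixes demographics and BMI, and the Covariates paragraph of Section D names PYD, SDQ and SRQ-Prosocial. Only the add-on rule is open, for want of a test, threshold or closed list.

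**Conclusion.** The point holds as a minor one. The plan compares arms on change from baseline and does not use the pre-randomization outcome as a covariate, although it could with no new data. Ignoring clustering, the SE would be 19% to 2.5% lower for rho from 0.3 to 0.9, and only about 1% lower for zBMI if rho is near 0.95. In the six-site design a gain is likely but not assured: at rho 0.5 the settings tabulated run from 9% lower to 8% higher. All of this rests on assumed correlations, and the magnitudes apply to the baseline-covariate model, not to the common-baseline alternative.

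The documents do not support a claim of bias or type I error inflation from this choice. The add-on covariate rule is a secondary gap in pre-specification; its effect on precision is small, with no consistent sign.

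**What to change.** In both parts of Section E, for each outcome, model the follow-up wave or waves with the youth-level baseline value of that outcome as a covariate, or use a longitudinal model with a common baseline mean across arms. Account for ASP clustering either way. Do not adjust for ASP baseline means: in a site-level analysis that spends one of four degrees of freedom and raises the 5% critical t value from 2.78 to 3.18. Keep the change-score analysis as a labelled sensitivity analysis, since youth-level adjustment can be the less precise when ICC and ASP-level correlation are both high.

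Secondarily, replace the add-on rule in both places with a closed list drawn from the Covariates paragraph of Section D, fixed before year-2 baseline data are seen.

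The cost is analysis-plan wording only; every variable is already to be collected.
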